6.3.6 Suicidality Assessment Using C-SSRS

Results of the C-SSRS, assessed at each visit, will be evaluated and reported according to the Columbia Classification Algorithm of Suicide Assessment (C-CASA) for the Safety Population.

6.4 Subgroup Analysis

Subset analysis will be stratified by anti-spasticity and MS medications used (ie, tizanidine, fampridine, etc) at Visit 1 if the percentage of subjects in these stratification groups is $\geq 10\%$ of the total number of subjects enrolled.

The effects of any other medications and/or medical conditions present at Visit 1 will also be explored. Should any medications be used by or conditions be present in 20% or more of the subjects overall, subjects will be stratified accordingly and the incidence of TEAEs in each part summarized.

The incidence of TEAEsh will be summarized by the following subgroups: sex, age (below 65 years of age and 65 years of age and older), and race.

30Oct2017

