## Statistical methods:

Descriptive statistics, including the numbers, means, standard deviations, medians, minimums, maximums and 95% confidence intervals for continuous variables and the numbers and percentages for categorical variables, will be provided. Listings of individual subject's data will also be produced.

Subset analysis will be stratified by concomitant anti-spasticity and MS medication used if the percentage of subjects in these stratification groups is  $\geq 10\%$  of the total number of subjects enrolled.

Confidential Page 4 of 47

	Day -14	Day 1	Day 28	Day 84	Day 182	
Activities	Week -2 Visit 1 (Screen) a	Week 1 Visit 2 (Baseline)	Week 4 ± 5 days Visit 3	Week 12 ± 5 days Visit 4	Week 26 ± 5 Days Visit 5 / Premature Termination Visit b	Visits Every 3 Months ± 5 days c
Informed consent	X	-	-	-	-	
Medical history and demographics	X	-	-	-	-	
Physical examination	X	-	-	-	X	
Neurologic examination	X	-	-	-	X	
Urine pregnancy test	X	-	X	X	X	X
Vital signs (sitting)	X	-	X	X	X	
Clinical laboratory tests d	X	-	-	-	X	
12-lead ECG e	X	-	X	X	X e	
C-SSRS	X	-	X	X	X	X
Concomitant medication and physical therapy assessments	X	X	X	X	X	X
AE evaluation	X	X	X	X	X	X
Dispense study medication	X	X	X	X	X	X
Collect study medication	-	X	X	X	X	X
Dispense / collect subject diaries	X	X	X	X	X	X
6 1 1 1 · · · · ·	77	37	7.7	7.7	77	***

Table 1: Visits and Procedures Schedule

X

X

Χ

X

X

X

Schedule next visit

Confidential Page 5 of 47

aScreening Visit assessments in CLR\_11\_04 which are identical to final visit assessments in CLR\_09\_21 do not need to be repeated. The Screening Visit may be completed simultaneously with the final visit for CLR\_09\_21, and on the following day, if needed, provided drug supply from CLR\_09\_21 does not run out. Subjects cannot enter CLR\_11\_04 if drug supply runs out prior to the completion of the screening process.

<sup>bFor subjects not completing the study, all activities scheduled at this visit are to be conducted during the Premature Termination visit with the exception of the ECG (see footnote "e" below) and the physical and neurologic examinations. These three assessments may be conducted during the Premature Termination visit as needed in order to follow the resolution of any adverse events.

<sup>cThese visits will be scheduled 90 (± 5) days following the previous visit.

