#### 12.3.3. Analysis of Safety Variables

#### 12.3.3.1. Adverse Events

All AEs will be coded in a standardized manner for regulatory activities. All AEs will be coded by system organ classification and preferred terms according to the Medical Dictionary for Regulatory Activities (MedDRA®). A AE is defined as: any new event that occurred after administration, a condition that existed before drug administration but increased in severity, or a condition that existed prior to drug treatment but increased in frequency of occurrence.

Medical history and physical examination anomalies that existed prior to Visit 1 will be considered baseline, abnormal, medical conditions, and will be described in the medical history or physical examination CRFs. These will be summarized separately.

The incidence of AEs and SAEs will be summarized by relationship to the trial treatment, by severity, and by action taken. In addition, separate summaries will be prepared with subjects categorized by sex, age (below 65 years of age and 65 years of age and older), and race.

Confidential Page 36 of 47

The effects of concomitant medications and/or medical conditions present at Visit 1 will also be explored. Should any medications be used by or conditions be present in 20% or more of the subjects overall, subjects will be categorized accordingly and the incidence of AEs in each part summarized.

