5.1.2 Safety Groups

5.1.2.1 Safety Group 1: Subjects who exited the Study CLR 09 21

Study CLR_11_04 will open for enrollment while study CLR_09_21 is ongoing. Blinded study medication will be temporarily dispensed to all subjects enrolled into CLR_11_04 who have exited study CLR_09_21

All potential subjects will review the informed consent document prior to receiving blinded
study medication kits dispensed via IVRS/IWRS. Kits dispensed will be similar in
appearance and packaging as dispensed during Part 3 of study CLR 09 21.
The actual identity of the contents
can be obtained only by breaking the blinding code.
During Visit 3, and for the remainder of this study, open label kits will be dispensed to all subjects who completed CLR_09_21.
5.1.2.2 Safety Group 2:
Subjects entering the trial complete a Screening period (Visit 1) of up to 14 days to allow all potential subjects to review the informed consent form and complete the procedures At Baseline (Visit 2), these subjects will start with

Subjects receiving other anti-spasticity medications will have the starting dose determined according to the investigator's medical judgment.

5.2 *P*-Values

Data presentations in this safety study will be descriptive. Unless stated otherwise, any significance tests will be two-sided with statistical significance assessed at the alpha (α) 5% level. All p-values will be reported to four decimal places. P-values will not be adjusted to account for multiple comparisons.

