6.1.5 Prior and Concomitant Medications

Prior and concomitant medications will be coded using the World Health Organization Drug Dictionary (WHODD) March 2012. These will be summarized overall and by Safety Group based on Anatomical Therapeutic Chemical Class 3 level (ATC 3), using incidence and percentage.

Neurological and anti-spasticity concomitant medications, identified before data lock, will be summarized separately overall, and for each Safety Group using incidence and percentage, and will be listed for all subjects.

Medications previously used (within 30 days of Visit 1) and before the on-study treatment will be considered Prior Medications. These will be summarized separately.

Physical therapy regimen will be summarized by visit using counts and percentages. Numbers of subjects with changes at post-baseline visits will also be summarized.

When medication start and/or stop dates are missing, the following imputations will be made (subject to medical review):

Missing Medication Start Dates

- 1. If onset date is completely missing, then onset date is set to date of first dose
- 2. If year is present and (month and day are missing), or (month is missing but day is present):
 - a. If year = year of first dose, then set date to first dose date

- b. If year < year of first dose and medication stop month and year are available, then set to first of the end month
- c. Otherwise if year < year of first dose, then set month and day to December 31st.
- d. If year > year of first dose, then set month and day to January 1st.
- 3. If month and year are present and day is missing:
 - a. If year=year of first dose and
 - i. If month = month of first dose then set day to day of first dose date
 - ii. If month < month of first dose then set day to last day of month
 - iii. If month > month of first dose then set day to first day of month
 - b. If year < year of first dose then set day to last day of month
 - c. If year > year of first dose then set day to first day of month
- 4. If the medication start date is completely missing and the corresponding stop date is completely missing, the medication start date will remain missing.

• Missing Medication Stop Dates

If the stop date is completely missing, the stop day will not be estimated (i.e., the medication will be assumed to be continuing).

If only the day of Medication stop is unknown, the day will be assumed to be the last day of the month (e.g. ??-JAN-2011 will be treated as 31-JAN-2011).

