Appendix 2: Planned Tables, Listings, and Figures

Table 14.1.1.1	Screen Failure Summary
Table 14.1.1.2	Protocol Deviations – Safety Population
Table 14.1.2	Subject Disposition – Safety Population
Table 14.1.3	Demographics – Safety Population
Table 14.1.4	Medical History – Safety Population
Table 14.1.5.1	Prior Medications – Safety Population
Table 14.1.5.2.1	Concomitant Medications – Safety Population
Table 14.1.5.2.2	Concomitant Medications – Anti-Spasticity - Safety Population
Table 14.1.5.2.3	Concomitant Medications – Neurological - Safety Population
Table 14.1.5.3	Physical Therapy Regimens – Safety Population
Table 14.1.6	Physical Examination Results – Safety Population
Table 14.1.7	Neurological Examination Results – Safety Population
Table 14.1.8.1.1	Exposure Duration – Safety Population
Table 14.1.8.1.2	Summary of Dosing by Dose Level and Visit – Safety Population
Table 14.1.8.1.3	Shift Table of Dosing by Dose Level and Visit – Safety Population
Table 14.1.8.2.1	Compliance – Safety Population
Table 14.1.8.2.2	Compliance as Assessed by Subject Diary – Safety Population
Table 14.3.1.1	Overview of Treatment-Emergent Adverse Events – Safety Population
Table 14.3.1.2	Treatment-Emergent Adverse Events by System Organ Class and Preferred Term – Safety Population
Table 14.3.1.3	Treatment-Emergent Adverse Events by Preferred Term – Safety Population
Table 14.3.1.4	Treatment-Emergent Adverse Events by System Organ Classand Preferred Term by Sex – Safety Population

Table 14.3.1.5	Treatment-Emergent Adverse Events by System Organ Class and Preferred Term by Age (<65 Years and ≥65 Years) – Safety Population
14010 14.5.1.5	Treatment-Emergent Adverse Events by System Organ Class and Preferred Term by
Table 14.3.1.6	Race – Safety Population
	Treatment-Emergent Adverse Events by System Organ Class, and Preferred Term by
	Medications Present in 20% or More of Overall Subjects at Visit 1 – Safety
Table 14.3.1.7.1	Population
	Treatment-Emergent Adverse Events by System Organ Class, Preferred Term by
Table 14.3.1.7.2	Medical Conditions Present in 20% or More of Overall at Visit 1 – Safety Population
	Treatment-Emergent Adverse Events by System Organ Class and Preferred Term by
Table 14 2 1 7 2	MS-Related Medications Taken by ≥ 10% of All Subjects at Visit 1 - Safety
Table 14.3.1.7.3	Population Treatment-Emergent Adverse Events by System Organ Class, Preferred Term and
Table 14.3.1.8	Severity – Safety Population

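### SAP 6.4 defines the 10% co-medication subsets by use at Visit 1, which precedes first dose in non-roll-over subjects, and the matching TEAE table title omits anti-spasticity drugs

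*SAP*

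**What the plan says.** **Subset definition.** SAP 6.4 states: "Subset analysis will be stratified by anti-spasticity and MS medications used (ie, tizanidine, fampridine, etc) at Visit 1". The subset is produced when a group reaches 10% "of the total number of subjects enrolled". The protocol synopsis, under Statistical methods, words it differently: "Subset analysis will be stratified by concomitant anti-spasticity and MS medication used", with the same 10% trigger and no mention of Visit 1. SAP Section 2 says the SAP prevails over the protocol's statistical section, so the Visit 1 definition governs.

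**The 20% rule.** For other drugs and conditions, SAP 6.4 uses a higher trigger: "Should any medications be used by or conditions be present in 20% or more of the subjects overall". Here the protocol does refer to Visit 1, in 12.3.3.1: "The effects of concomitant medications and/or medical conditions present at Visit 1 will also be explored".

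**When study drug starts.** SAP 4.2.1 counts study days from Visit 1 for roll-over subjects and from Visit 2 for the others. On the interval between those visits, SAP 5.1.2 says: "Subjects entering the trial complete a Screening period (Visit 1) of up to 14 days".

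**Prior versus concomitant.** SAP 6.1.5 says: "Medications previously used (within 30 days of Visit 1) and before the on-study treatment will be considered Prior Medications". It then decides prior or concomitant status relative to study drug treatment, from imputed start and stop dates.

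**Planned output.** In SAP Appendix 2 the only TEAE table with a 10% rule is 14.3.1.7.3, whose title reads in part: "MS-Related Medications Taken by ≥ 10% of All Subjects at Visit 1". Table 14.3.1.7.1 covers medications at 20% or more. Table 14.1.5.2.2 reports concomitant anti-spasticity drugs as a class of their own, but gives use and no TEAEs.

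**The concern.** Two things do not line up.

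The first is timing. The purpose of these subsets is to show how study drug is tolerated alongside other anti-spasticity or MS drugs. For a non-roll-over subject, use at Visit 1 is recorded before any study drug is taken. If the other drug is stopped when study drug starts, the subject is never co-medicated with it, yet sits in the user stratum. Such subjects pull the user/non-user contrast toward no difference and help a drug reach the 10% trigger. SAP 6.1.5 and 6.4 would classify the same medication record in opposite ways. The SAP does not mention or explain its move from concomitant to Visit 1.

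The second is output. The text of 6.4 promises the 10% rule for two drug classes, and the table title names one. A programmer working from the title could leave out anti-spasticity drugs, the class closest in purpose to the study drug. No listed TEAE table is split by co-medication taken during treatment, so nothing else fills the gap. Safety is this trial's only objective.

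**Working it through.** The documents derive no figure for these subsets, so there is nothing to reproduce. The check compares the sections, counts subjects at the thresholds, and shows which quantities would be needed to size the dilution.

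**1. Visit 1 relative to first dose**

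| Subject type | Study drug starts (SAP 4.2.1) | Gap from Visit 1 |
|---|---|---|
| Roll-over | Visit 1 | none |
| Non-roll-over | Visit 2 | up to 14 days (SAP 5.1.2) |

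**2. One record followed through the SAP.** Take a non-roll-over subject using a qualifying drug at Visit 1, with a stop date before the first dose at Visit 2.

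- SAP 6.1.5: prior medication.
- SAP 6.4: user at Visit 1, counted in the user stratum and toward 10%.

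For a roll-over subject the two classifications agree at entry, because Visit 1 is the start of study drug.

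**3. Dilution in algebra.** Let p1 and p0 be the TEAE incidences with and without the co-medication. Let d be the share of Visit 1 users no longer on the drug at first dose, and s the share of Visit 1 non-users who have started it by then. Assume incidence depends only on true use.

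- User stratum: (1 − d)·p1 + d·p0
- Non-user stratum: s·p1 + (1 − s)·p0
- Observed difference: (p1 − p0)·(1 − d − s)

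The factor 1 − d − s at assumed values, for illustration only:

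| d | s | Factor |
|---|---|---|
| 0.10 | 0 | 0.90 |
| 0.20 | 0 | 0.80 |
| 0.30 | 0 | 0.70 |
| 0.10 | 0.05 | 0.85 |
| 0.20 | 0.10 | 0.70 |
| 0.30 | 0.20 | 0.50 |

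Neither d nor s is in the documents. Moreover, d is an average over the whole user stratum. If roll-over users contribute essentially none, d equals the non-roll-over share of users times the stopping share among them, and neither component is given. The direction is clear; the size cannot be computed.

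**4. Subject counts at the thresholds.** The protocol plans 350 enrolled and the SAP 550, so both are shown.

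- N = 350: 0.10 × 350 = 35 and 0.20 × 350 = 70, so 10% to under 20% is 35 to 69 subjects.
- N = 550: 0.10 × 550 = 55 and 0.20 × 550 = 110, so 10% to under 20% is 55 to 109 subjects.

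**5. TEAE table by drug class, reading Appendix 2 titles literally**

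| Drug class | 10% to under 20% | 20% or more |
|---|---|---|
| MS-related | 14.3.1.7.3 | 14.3.1.7.3 |
| Anti-spasticity | none | 14.3.1.7.1 |
| Other | none, and none promised | 14.3.1.7.1 |

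The middle row conflicts with SAP 6.4, which promises the 10% rule for anti-spasticity drugs.

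**The case against.** The case for leaving the plan alone has several parts.

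- *Strata fixed at baseline are sound.* They avoid conditioning on post-baseline behaviour. This stands, and is why the change proposed here keeps a baseline stratum.
- *A drug in use at Visit 1 and continued is true co-medication.* This stands. A reader might infer that the strata say nothing about TEAEs under co-medication. The documents do not support that: no readable passage requires the example drugs in 6.4 to be stopped at first dose, and protocol 9.3 only asks that concomitant treatments be recorded.
- *The affected group may be small.* The timing problem touches only non-roll-over subjects. Protocol inclusion criterion 6 admits only completers of CLR_09_21, whereas the SAP plans for two further safety groups. Their share is not stated.
- *The protocol itself ties concomitant drugs to Visit 1 in 12.3.3.1.* This is true for the 20% rule, so the SAP does not depart from the protocol there. Protocol 12.3.5, on subsets, is partly blacked out and settles nothing.
- *The table title may be shorthand.* Every subject has spasticity due to MS, the term MS-related is undefined, the shells are not in the documents, and SAP 5.5 commits to every analysis the SAP outlines. The omission is therefore a literal reading and not a proven intention. It remains an ambiguity that a title change removes.
- *The analysis is descriptive (SAP 5.2), and dated listings permit case review.* This limits the consequence but does not reconcile 6.1.5 with 6.4.

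**Conclusion.** The point holds in two limited parts.

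1. For non-roll-over subjects, the 10% subsets in SAP 6.4 classify use up to 14 days before first dose and can disagree with SAP 6.1.5. For them the strata are a diluted proxy for co-medication. The bias is toward no difference, assuming TEAE incidence depends on actual use. Any stated shrinkage in percentage points would rest on invented incidences and stopping rates, and none is claimed here.
2. Taken literally, Table 14.3.1.7.3 leaves an anti-spasticity drug used by 10% to under 20% of subjects (35 to 69 of 350, or 55 to 109 of 550) without the TEAE table that 6.4 promises. A reader might conclude that the plan drops anti-spasticity drugs altogether. It does not: at 20% or more, the title of Table 14.3.1.7.1 can carry them.

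Roll-over subjects are unaffected by the first part, and the 20% rule agrees with the protocol. The consequence is modest, but so is the cost of correction, and it should be made before the programs are final.

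**What to change.** - In SAP 6.4 and Table 14.3.1.7.3, define the 10% subset as anti-spasticity or MS medication ongoing at the first dose of study drug, using the imputed start and stop dates in 6.1.5. Apply the 10% trigger to that count.
- Retitle Table 14.3.1.7.3 so that it names *Anti-Spasticity and MS Medications*.
- Leave the 20% rule at Visit 1, as protocol 12.3.3.1 has it, or change both documents together.
- Add a sentence to 6.4 saying why the definition differs from the synopsis, that this remains a baseline stratum, and that it does not capture later starts or stops.
- State how records with both dates missing are handled, since 6.1.5 leaves their start date missing. Note also that a stop date lacking only the day is set to the end of the month, so a drug stopped during screening can still appear ongoing at first dose.

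The cost is SAP wording and one changed selection rule; the dates are already planned for collection. User strata become slightly smaller, and there may be one more table panel. Classification of roll-over subjects hardly changes.

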7. TESTING/QUALITY CONTROL PLAN AND SOFTWARE/SYSTEM

All statistical programs will be written in SAS® version 9.3, or later. Statistical programs will be tested and reviewed for Quality Control (QC) by a second programmer/biostatistician not involved in the programming as per standard operating procedure (SOP). In addition, SOP will be followed to ensure that the information is complete, consistent, and accurately reflects the data stored in the Clinical Data Management System (CDMS) database. Further all tables, listings, and figures (TLFs) will undergo a QC process by an independent biostatistician/programmer to ensure that the information is complete, consistent with the analysis methods described in this SAP, and accurately reflects the data stored in CDMS.

7.1 Programming Specifications for TLFs

Appendix 1 provides a list of the TLFs that are planned to be produced.

7.2 Formatting Conventions

The following formatting conventions will be used to output TLFs:

- TLFs are outputted by SAS Output Delivery System (ODS) into Rich Text Files (RTF) format.
- Tables and Listings will include borders around all headings and data cells.
- Output will be in landscape orientation with margins of 1.5 inches on top, and 1 inch for right, left, and bottom.
- The default font to be in tables/listings/figures will be Courier New.
- Preferred and minimum font size:

Portion of Output	Preferred	Minimum
Page Header	10 pt	8 pt
Title	10 pt	8 pt
Column header	10 pt	8 pt
Cells	10 pt	8 pt
Footnote	10 pt	8 pt
Page Footer	10 pt	8 pt

- Data will be centered within columns when the maximum length of the data being displayed is less than or equal to the maximum width of the column heading. When the maximum length of the data being displayed exceeds the maximum width of the column heading, the data will be left-justified.
- Column headings should be in initial capital characters. For numeric variables, include "unit" in the column heading when appropriate.
- In figures, axes will be labeled appropriately.

Version 1.0

30Oct2017

7.3 Standard Text Conventions

7.3.1 Header

All output (table, listing, or figure) will have the following header:

Sun Pharma Advanced Research Company Ltd.

Protocol CLR 11 04

Page xx of XX

All output will have the date and time (date and time output was generated) and internal page number in the footer. Tables/Listings/Figures should be internally paginated (i.e., page numbers should appear sequentially within each output).

7.3.2 **Title**

At least three (3) lines, in general, will be reserved for the entire title.

- The first line is for the table/listing/figure number;
- The second line is for the actual title; and
- The third line is reserved for the analysis population descriptor.
 - Population(s) represented on the tables will be clearly identified in the last row of the table Title. Consistent terminology will be used to identify a population.
 - Sub-population(s) or special population(s) descriptions will provide sufficient detail to ensure comprehension of the population (e.g., Safety Group 1 Subjects from Study Site 1, Safety Group 2 Subjects from Study Site 2) used for analysis in a table, figure, or a data listing.

All titles will be centered, as shown in the following example:

Table 14.3.2.1 Overall Incidence of Safety Events Safety Population

7.3.3 Footnotes

Unless otherwise specified, footnotes will appear on all pages within the tables and listings as follows:

• Footnotes will be in the format of "Note: followed by 2 spaces, then the footnotes", as shown in the following example:

Note: SD = Standard Deviation; SEM = Standard Error of the Mean.

- Each line of a complete footnote should end with a period.
- When an abbreviation (e.g. AE, SAE, etc.) appears for the first time in the whole set of TLFs for a study, a footnote should be provided at least once; and it is up to the study statistician to decide whether there is a need to repeat the same footnote for the rest of TLFs.
- A footnote serves as a brief explanation/clarification /definition /concept of a flag symbol or a character, an abbreviation, a terminology, etc., that appears in or relates directly to the displayed content of a table/listing/figure.
- All footnotes will be at the lowest line of the page immediately above the footer. There will be one space between the last footnote and the footer.
- For Tables, first footnote will provide source listings and/or analysis datasets names for cross-referencing.

